breastfeeding mother and the baby. Ketamine and its metabolites will be evaluated in PND patients receiving ketamine 0.5 mg/kg or 0.2 mg/kg at 30 mins, 2 hours and 4-5 hrs after ketamine infusion. All adverse medical and psychiatric events with onset or worsening after the administration of ketamine will be included in the analysis.

The proposed experiment will be a proof-of-concept study in which we will evaluate the safety, pharmacokinetics, and efficacy of ketamine 0.5 mg/kg and 0.2 mg/kg over 40 minutes in a double-blinded and crossover fashion separated over one week (5) (dose used in antidepressant clinical trials) in PND patients who are not currently breastfeeding. The primary outcome measure of efficacy will be the Hamilton Depression Rating Scale (HAM-D-17) at 24 hours and additional secondary anxiety and mood scales. (6). Any adverse medical and psychiatric events will be recorded and summarized. Ketamine and its metabolites will be evaluated at 30 mins, 2 hours and 24 hrs.

Hypothesis 1): Ketamine will significantly decrease (>50%) in HAM-D17 scores at 24 hrs after infusion from baseline. The 0.5 mg/kg dose will be more efficacious than 0.2 mg/kg in improving depression symptoms.

Hypothesis 2) Ketamine will improve anxiety symptoms in PND (as measured using HAM-Anxiety and EPDS) at 24 hrs after infusion in patients with PND. Anxious subtypes are the most common subtype during a late postpartum period representing about 70 % of PND. (40)

Hypothesis 3) Ketamine infusion will be tolerated well by the patients with fewer side effects at 0.2 mg/kg compared to 0.5 mg/kg.

METHODS

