Before the infusion, the psychiatrist and anesthesiologist will evaluate the patient. During the infusion, patients will be asked constantly about "how they feel" and will be monitored continuously by the registered nurse under the supervision of an Anesthesiologist. EKG and pulse-oximetry will be monitored throughout the procedure to

check for hemodynamic changes. After the completion of 40 min infusion, patients will rest for two-four hours under the observation of clinical nurse.. After the infusion both psychiatrist and anesthesiologist will evaluate the patient. Patients may complete clinical questionnaires after this session at HCPC or CRU for approximately 30 minutes. After the first infusion, patients will be contacted one day after over the phone and after the second infusion, patients will be contacted one day after and 7 days after the infusion. During the phone call, patients will be asked about their physical health, will be asked about adverse events and respond questionnaires that evaluate mood status.

Recruitment: The current project will ensure robust and timely recruitment through coordination with ongoing studies at the UT Center of Excellence on Mood Disorder (CEMD) ([name], Departmental Chair). [name] runs a perinatal clinic focused on pregnant or postpartum women with mood disorders in the psychiatry department. [name] also collaborates with [name], UTHealth Department of Obstetrics, Gynecology and Reproductive Sciences on a postpartum research project. Additionally, a large research participant registry has been set up by this UT center (n = 4952 over the last 5 years, of which 80% have a mood disorder history).

Recruitment will also be facilitated through the UT Research Match program. On average, 200 patients have a higher report of depression and mental health problems in the last year and of which nearly 100 patients had higher EPDS scores that meet PND criteria. The perinatal psychiatry clinic will facilitate clinical recruitment. Subject recruitment will include initial identification of cohort pool using selection criteria and subsequent review of identified patient records before final vetting and consent.

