Ketamine infusion: The most commonly reported side effects during the 4 hour period after each infusion include feeling strange or unreal (58.3%), abnormal sensations (54.2%), blurred vision (50.0%), feeling sleepy or sleepy (48.5%) and headaches (30-40%). Based on previous evidence, we do not expect ketamine to impair

cognitive functions such as memory, attention or language. If patients are currently taking certain medications on a daily basis within 24 hours prior to and/or after receiving ketamine, they will not be able to take these medication(s) while receiving a ketamine infusion without clearance or approval of the physicians involved in administering ketamine. Medications include: Sedatives (e.g., clonazepam, lorazepam, alprazolam); Antibiotics (e.g., azithromycin, clarithromycin); Antifungal agents (e.g., ketoconazole); Tramadol. This is due to concerns for potentially increased sedation or trouble breathing. One third of the patients exposed to standard repeated infusions of IV ketamine reported some kind of hemodynamic change such as elevated blood pressure (BP) and/or heart rate (Murrough et al., 2013b) that usually resolves shortly after the ketamine infusion (aan het Rot et al., 2010; Murrough et al., 2013b). It has been reported that initial hypertensive episodes and transient tachycardia are predictive of hemodynamic changes with subsequently repeated ketamine infusions (aan het Rot et al., 2010). Ventricular premature contractions, hypotension, and non-significant changes in oxygen saturation have also been reported with low-dose (0.5mg/kg) ketamine infusions over 40 minutes.

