Patients considered as participants of the study will be referred to [name] as a treating psychiatrist if they are not his patients. Patients who are referred by existing providers will return under the care of their care. If they have successful treatment with ketamine, they will be referred to a list of providers in the area of Houston that provide ketamine infusions as treatment for depressive symptoms, if the patient would want to consider continuing with the treatment as needed.

Data and Safety Monitoring Plan

The principal investigator will be responsible for the Data and Safety monitoring of the study.

Data monitoring plan

Data will be collected and stored as described above in Sources of Material and analyzed with primary outcomes as described in the Statistical Plan. Trained research assistants will enter data into an existing, relational database. Allowable input values will be restricted to standardized Access entry forms so as to maintain data integrity. All observations will be double-entered to verify the accuracy, with any problems detected discussed with the PI. If necessary, the re-training of research assistants will be conducted. Due to the comparatively small and initial nature of the current trial, interim data analysis is not planned.

Safety monitoring plan

During the screening, study applicants will undergo a complete psychological and physical exam to determine their eligibility and safety of their participation in this study, per inclusion/exclusion criteria detailed above. During the treatment phase of the study, participants will be asked about adverse events at each clinic visit and vital signs will be continuously monitored during the infusion and two hours after the infusion.

All adverse events (AEs) occurring during the course of the study will be collected, documented, and reported to the Principal Investigator. The occurrence of AEs will be assessed at baseline and each visit during the treatment phase of the study. The PI, in consultation with the co-investigators, will review any AE's as soon as they are reported. The study investigators will follow all AEs to the point of a satisfactory resolution. A study participant may have their medication discontinued or may be withdrawn from the study if the Study Physician determines it is the best decision in order to protect the safety of a participant. All AEs will be assessed to determine if they meet criteria for an SAE.

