DATA ANALYSIS PLAN - General Data Analysis: The data analytic strategy will use generalized linear modeling. Statistical analyses will use SAS v.9.3. Preliminary data analyses will inspect baseline, treatment from baseline differences as well as correlations between baseline variables and specified outcomes. Baseline characteristics will be compared within groups using Student's t-tests for continuous data and chi-square tests for categorical data.

Sample size justification: our power calculation is guided by a previous study - intravenous ketamine in TRD patients (28) with effect size (Cohen's $d = 1.46$) or Brexanolone in PND (effect size 1.2) (12, 32). For an effect size 1.2, a total of 10 PND patients will be required for within-subject design with probability 95 % that the study will detect a treatment difference at a one-sided 0.05 significance level.

Hypothesis: Based on previous studies (33, 34) and our pilot Ketamine TRD patient data, we predict that ketamine infusion compared to baseline will significantly decrease HAM-D scores in PND patient at 24 hrs. The severe anxious subtype will have prominent improvement.

Analysis: We will use linear regression to assess associations between improvements in depressive symptoms (change in the HAM-D from baseline using LOCF). A paired t-test was performed to evaluate the key efficacy measure - change from baseline in HAMD total score. We will also perform a secondary analysis comparing change from baseline to endpoint using last observation carried forward (LOCF) using a paired sample t-test. Secondary outcomes are safety and tolerability measures, including treatment-emergent AEs and changes from EPDS, GAD-7, PHQ-9, and C-SSRS. We will also investigate specific markers for treatment response.

Alternate plans: The proposal applies the widely used ketamine sub-anesthetic dose (0.5 mg/kg) as a treatment for PND. If the effect is less clear or patient experiences any adverse effects, alternate strategies will be explored (two doses of ketamine instead of single or low dose 0.3 mg/kg if adverse effects etc. respectively). Patient safety and tolerability will be the most important guiding principle. This will require an amendment in the protocol and an updated consent.

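### Blood pressure, heart rate and oxygen saturation are to be monitored at each infusion for a known ketamine effect, but the plan has no summary or dose comparison of them, so they reach the results only if labelled an adverse event

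*Combined protocol and SAP*

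**What the plan says.** - **Known effect.** Potential Risks/Discomforts, Ketamine infusion: "One third of the patients exposed to standard repeated infusions of IV ketamine reported some kind of hemodynamic change such as elevated blood pressure" and/or heart rate. The same paragraph adds ventricular premature contractions, hypotension and non-significant saturation changes at 0.5 mg/kg.
- **Monitoring.** Research Design and Methods: "EKG and pulse-oximetry will be monitored throughout the procedure to" look for hemodynamic changes. Safety monitoring plan: "vital signs will be continuously monitored during the infusion and two hours after the infusion". Data Handling and Record Keeping again promises strict hemodynamic and respiratory monitoring at each infusion.
- **Schedule.** The assessment table, as extracted, marks vital signs at screening and before each infusion, with no mark after an infusion.
- **Goal.** Hypothesis 3: "Ketamine infusion will be tolerated well by the patients with fewer side effects at 0.2 mg/kg compared to 0.5 mg/kg". Research Design and Methods says that giving two doses will help decide which is safe, tolerable and effective. The Justification makes safety part of the primary goal and omits placebo because the aim is to learn whether the lower dose works as well with fewer side effects.
- **Analysis.** The Data Analysis Plan lists: "Secondary outcomes are safety and tolerability measures, including treatment-emergent AEs and changes from EPDS, GAD-7, PHQ-9, and C-SSRS". Specific Aims adds that adverse events will be recorded, summarized and included in the analysis. No section gives a summary measure, time window, cut-off or dose comparison for blood pressure, heart rate, EKG or saturation.

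**The concern.** The trial gives both doses to each woman partly to compare their tolerability. The readings that bear most directly on the hemodynamic effect named in the protocol are taken at the bedside, but the plan does not carry them into the results. What remains is the adverse-event record, and nothing says what size of change counts as an event. The protocol describes these changes as usually resolving soon after the infusion, so one clinician might record such a change and another might regard it as expected. The dose comparison of hemodynamic effects would then depend partly on labelling habits. If the readings are watched but never written to a trial record, they cannot be recovered for analysis later.

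**Working it through.** **1. The plan's own figure.** The sample-size statement reads "For an effect size 1.2, a total of 10 PND patients will be required for within-subject design"; it sets power at 95% and a one-sided test at the 5% level. For a paired t-test, power = P(T > t(0.95, n−1)), where T is noncentral t with n−1 degrees of freedom and noncentrality d√n.
- n = 9: noncentrality 1.2 × √9 = 3.60, power 94.8%.
- n = 10: noncentrality 1.2 × √10 = 3.79, power 96.7%.

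The smallest n reaching 95% is 10, so the stated figure reproduces. It concerns efficacy only; no safety comparison was sized.

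**2. Measures monitored against measures analysed.**

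| Measure | Monitoring or collection | Planned analysis |
|---|---|---|
| Vital signs (blood pressure and heart rate taken as included) | During infusion and 2 h after (Safety monitoring plan); schedule marks only screening and pre-infusion | None |
| Pulse-oximetry | Throughout the procedure (Research Design and Methods) | None |
| EKG | Throughout the procedure | None |
| BPRS | Screening and after each infusion | None |
| Adverse events | Screening, after each infusion, follow-up calls | Listed; no dose comparison specified |
| C-SSRS | Screening and after each infusion | Listed |
| EPDS, GAD-7 | Screening, before and after each infusion, follow-up calls | Listed |

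The adverse-event row is the only route by which a hemodynamic change can enter the results.

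**3. How much the labelling could matter (illustration).** Input: one third, from Potential Risks/Discomforts. That rate is for repeated infusions; applying it to one infusion is an assumption. The fraction q of changes labelled as adverse events is not in the documents and is shown as a range.
- Expected number of women with a change at one infusion: 10 × 1/3 = 3.3.
- Chance of at least one: 1 − (2/3)^10 = 98.3%.
- Expected labelled events = 10 × q/3; chance that none is labelled = (1 − q/3)^10.

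| q | Expected labelled events | Chance that none is labelled |
|---|---|---|
| 100% | 3.3 | 1.7% |
| 50% | 1.7 | 16% |
| 25% | 0.8 | 42% |

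**4. What a continuous summary would give.** The half-width of the 95% interval for a within-patient dose difference, in SDs of that difference, is t(0.975, df)/√10.
- Simple paired (9 df): 2.262/3.162 = 0.72.
- Adjusted for period, five women per order (8 df): 2.306/3.162 = 0.73.

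This is wide, but it uses the size of every woman's change and does not depend on labelling.

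**The case against.** **An adverse-event route exists.** All medical and psychiatric events with onset or worsening after ketamine enter the analysis, dosing is double-blind, and a nurse under an anesthesiologist watches for hemodynamic change. Hypothesis 3 speaks of side effects, not monitor readings. This stands: the effect is not shut out of the results. What is missing is a rule for which readings count and any summary of their size.

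**The safety list is open and partly sound.** A reader might infer that mood scales have replaced safety measures. The text does not support that: adverse events come first, C-SSRS is a genuine suicidality measure, and the list is worded as non-exhaustive. Moving EPDS, GAD-7 and PHQ-9 to another heading would change no result. But an open list that specifies nothing for vital signs is still silent on them.

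**Monitored is not recorded.** This also stands. The documents promise bedside surveillance and do not establish a dataset, so the remedy needs some data capture as well as analysis wording. The extracted schedule may be broken, but nothing elsewhere supplies post-infusion recording.

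**A power contrast is tempting but unsupported.** A reader might infer that the adverse-event route has almost no power and a continuous measure has plenty. For example, an exact paired test with one third against zero events has one-sided power of 21%. The documents do not support the contrast:
- The one-third rate is for repeated infusions, and no such test is planned.
- Side effects listed at 58.3%, 54.2% and 50.0% would give 80%, 72% and 62% under the same scenario.
- No standardised difference is given for the continuous measure. At assumed values of 0.5, 0.75 and 1.0, a two-sided 0.05 comparison with 8 df has power of only about 29%, 55% and 79%.

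**BPRS.** A reader might infer that BPRS captures acute drug effects. No section makes that link, and no BPRS is scheduled immediately before an infusion.

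**Conclusion.** The gap is real and rests on the text: a named effect, required monitoring, a stated aim of comparing doses on side effects, and no planned summary of the readings. Hemodynamic change reaches the results only through adverse-event labelling without a cut-off. In the illustration, the chance that it leaves no trace ranges from 1.7% to 42%; this assumes that the one-third rate applies to one infusion and that 25% to 100% of changes are labelled.

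The documents do not support the stronger inference that the two doses could be called similarly tolerated whatever the monitors showed, because blinded clinicians watch for these changes and adverse events are analysed. This is a worthwhile, inexpensive improvement to a 10-patient proof-of-concept study. It does not affect the primary efficacy result, and the added summaries would be descriptive, not a powered test.

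**What to change.** 1. **Capture.** Enter the already-monitored readings on the case report form, and reconcile the assessment schedule with the Safety monitoring plan on post-infusion vital signs.
2. **Outcomes.** In the Data Analysis Plan, add as descriptive safety outcomes, per infusion: peak change from that infusion's pre-infusion value in systolic blood pressure, diastolic blood pressure and heart rate, from infusion start to 2 h after (the period in the Safety monitoring plan); and lowest oxygen saturation over the period in which oximetry is actually monitored. The two-hour extension is stated only for vital signs, so the saturation window should be written down and be the same for both doses.
3. **Reporting.** Give each outcome by dose, with the within-patient 0.5 minus 0.2 mg/kg difference and its 95% confidence interval, adjusted for period, alongside adverse events by dose. Say that these are descriptive. Post-infusion BPRS may be summarised by dose as a descriptive item only.

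**Cost.** Modest data entry, one extra table and wide intervals (about 0.7 SD either side). No dose, visit or clinical rule changes.

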JUSTIFICATION - Research in PND is of critical importance due to its substantial burden on mother, family and child's emotional, cognitive and behavioral development. Rapid and effective treatment of severe PND is a significant unmet need. The primary goal of the project is to evaluate the safety and efficacy of sub-anesthetic antidepressant dose ketamine treatment in severe PND patients. This proposal will be the first systematic investigation of ketamine's antidepressant effect in PND. The study design is simple and robust that can provide

early treatment response signal without significant additional discomfort for patients. The results from this pilot proposal could potentially yield critical information regarding markers of treatment response in PND - a potentially high impact research area. the

Having a placebo group in this research project would not be warranted at this place since the aim is to determine if a lower ketamine dose would be as effective and with lower side effects for PND patients.

Data Handling and Record Keeping

This study will acquire, use and create individually identifiable health information (known as Protected Health Information or PHI). Confidentiality will be protected at all times by having research records identified by code number only. All research information will be stored in locked files at all times. Only authorized research staff will have access to the information gathered in this study. Only subjects capable of providing consent will be included in the study.

As per the Health Insurance Portability and Accountability Act (HIPAA), all individuals who are eligible and agree to participate in this research study will be required to sign a HIPAA research authorization prior to participation. If an individual refuses to sign the HIPAA research authorization, they will not be able to participate in this study. The HIPAA form is part of the official consent form.

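### The dose hypothesis and the no-placebo rationale are not aligned on efficacy, the analysis plan tests neither, and 10 patients could not support an equal-efficacy conclusion except at a very wide margin

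*Combined protocol and SAP*

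**What the plan says.** Four parts of the combined protocol and SAP bear on the dose comparison.

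- **PRIMARY HYPOTHESES AND SPECIFIC AIMS.** Hypothesis 1 ends with a directional prediction on efficacy: "The 0.5 mg/kg dose will be more efficacious than 0.2 mg/kg in improving depression symptoms". Hypothesis 3 makes a prediction on tolerability: "Ketamine infusion will be tolerated well by the patients with fewer side effects at 0.2 mg/kg compared to 0.5 mg/kg".
- **METHODS, Research Design and Methods.** Every patient receives both doses, double-blind, at least 7 days apart, in randomized and balanced order. The section says that having two doses will help in choosing one.
- **JUSTIFICATION.** A placebo group is judged unwarranted because "the aim is to determine if a lower ketamine dose would be as effective and with lower side effects for PND patients". The documents give no other reason for omitting placebo.
- **DATA ANALYSIS PLAN.** The hypothesis here is a comparison with baseline: "we predict that ketamine infusion compared to baseline will significantly decrease HAM-D scores in PND patient at 24 hrs". The test follows it: "A paired t-test was performed to evaluate the key efficacy measure - change from baseline in HAMD total score". The sample size sentence reads "For an effect size 1.2, a total of 10 PND patients will be required for within-subject design with probability 95" per cent, to "detect a treatment difference at a one-sided 0.05 significance level". Its effect sizes are 1.46, from intravenous ketamine in treatment-resistant depression, "or Brexanolone in PND (effect size 1.2").

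**The concern.** Predicting that the higher dose is better calls for a superiority contrast. Asking whether the lower dose is as good calls for a margin, or at least a stated precision. The crossover is built to compare the doses, yet the analysis plan supplies neither tool. Any statement on relative efficacy would therefore come from an analysis chosen later, and could be judged against either section.

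The risk is lopsided. With 10 patients, a non-significant dose difference is likely even if the higher dose is moderately better. Set beside the no-placebo rationale, that result could be taken as support for the lower dose when it mainly reflects low precision. At stake is an unsupported dose conclusion carried into later work.

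**Working it through.** **Inputs from the documents:** n = 10; within-subject design; one-sided alpha 0.05; target power 95%; effect size 1.2 (or 1.46).

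**Inputs not in the documents, so assumed:** the true dose difference (0.3 to 0.8 SD), the margin (0.3 to 1.2 SD) and the SD of the within-patient dose difference (4 to 8 HAM-D points, used only for conversion to points). SD below always means the SD of that paired difference. All results assume 10 completers and no carryover.

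**1. The plan's own figure.** Paired t-test power is the probability that a noncentral t with n − 1 df and noncentrality d√n exceeds t(0.95, n − 1). For d = 1.2 and n = 10:
- noncentrality = 1.2 × 3.162 = 3.79
- critical value t(0.95, 9) = 1.833
- power = 0.967

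Ten is the smallest n with at least 95% power, so the stated sample size reproduces. It rests on drug-effect sizes from other studies. The plan gives no effect size for 0.5 versus 0.2 mg/kg.

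**2. Precision of the dose difference.** The 95% half-width is t(0.975, 9)/√10 = 2.262/3.162 = 0.715 SD. Even if the observed difference were exactly zero, the interval would run from about −0.72 to +0.72 SD. At an assumed SD of 4 to 8 points, that is ±2.9 to ±5.7 HAM-D points (0.715 × 4 and 0.715 × 8). Fitting period costs one df: t(0.975, 8)/√10 = 2.306/3.162 = 0.73 SD with five patients per sequence.

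**3. Chance of missing a true advantage of the higher dose.** This applies the plan's alpha to a contrast that the plan does not specify.

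| True difference (SD) | Noncentrality | Power | Missed |
|---|---|---|---|
| 0.3 | 0.95 | 0.222 | 78% |
| 0.5 | 1.58 | 0.427 | 57% |
| 0.8 | 2.53 | 0.754 | 25% |

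**4. What non-inferiority would need.** With a true difference of zero, the power at margin m is the formula in step 1 with d replaced by m.

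| Margin (SD) | Power, n = 10, one-sided 0.05 | Patients for 80% power |
|---|---|---|
| 0.3 | 22% | 71 |
| 0.5 | 43% | 27 |
| 0.8 | 75% | 12 |
| 1.0 | 90% | 8 |
| 1.2 | 97% | 6 |

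Solving for 80% power at n = 10 gives a margin of 0.853 SD. At an assumed SD of 4 to 8 points, that is 3.4 to 6.8 HAM-D points. At one-sided 0.025 the margin for 80% power rises to about 1.0 SD.

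**The case against.** The strongest reply is that there is no contradiction. The JUSTIFICATION sentence asks an open question and does not claim to show equal efficacy. A trial may ask whether a lower dose is as good while predicting that it is not. The sentence explains a design choice, and the same section gives the primary goal as evaluating the safety and efficacy of ketamine. The study is described as a pilot and proof of concept, where a formal margin is not automatically expected. The general analysis paragraph also names generalized linear modeling, which could hold a dose term.

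Much of this stands. A reader might infer two opposite aims, but the wording supports only a misalignment, and only on efficacy. A reader might also infer that the sponsor intends to report non-significance as equal efficacy. No section says so. And a reader might take Hypothesis 1 to come with a superiority test that could simply be kept, but the analysis plan contains none.

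What does not stand is the idea that pilot status settles the matter. It argues for estimation with an interval, and the plan does not specify that for the dose difference. Naming a model family is not naming a contrast. Deciding whether one dose is as effective as another still needs a margin or a precision criterion.

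**Conclusion.** The concern holds as a failure to align the objectives and as a missing analysis. A plan followed to the letter would report improvement from baseline and leave both dose-efficacy questions unanswered.

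Ten pairs would leave a moderate advantage of the higher dose undetected more often than not, and could establish non-inferiority with reasonable power only at a margin of roughly 0.85 SD or wider. Dropout would reduce precision further, and carryover could bias the contrast.

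The sample size calculation is not in error. It is correct for its stated inputs, and would serve the dose contrast only if that difference were as large as 1.2 SD, which the documents give no reason to expect. The misreading of a non-significant result is a risk left open, not a rule in the plan. The point should be corrected but does not undermine the trial.

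**What to change.** - State one objective for the dose comparison and make Hypothesis 1, the DATA ANALYSIS PLAN and the JUSTIFICATION agree with it. The no-placebo rationale must be revised too, because it now rests on the efficacy question that the plan does not analyse.
- Specify in the DATA ANALYSIS PLAN the within-patient 0.5 versus 0.2 mg/kg difference in 24-hour HAM-D-17, with period in the model, reported with its 95% confidence interval beside the paired difference in adverse events.
- State that a non-significant dose difference will not be reported as equal efficacy.

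If the sponsor prefers to keep an equal-efficacy objective, it needs a justified margin and a sample size to match. The second table shows what that implies.

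**Cost:** one added analysis on data already scheduled, and a more modest conclusion on dose. The estimation route needs no extra patients, visits or change to dosing.
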